APPENDIX B: DURVALUMAB DOSE CALCULATIONS

Durvalumab Dosing

The durvalumab dosing should be done depending on subject weight (if subject is < 30kg) at 20 mg/kg:

1. Cohort dose: X mg/kg
2. Subject weight: Y kg
3. Dose for subject: XY mg = X (mg/kg) × Y (kg)
4. Dose to be added into infusion bag:

Dose (mL) = XY mg / 50 (mg/mL)

where 50 mg/mL is durvalumab nominal concentration

The corresponding volume of durvalumab should be rounded to the nearest tenth mL (0.1 mL). Dose adjustments for each cycle only needed for greater than 10% change in weight.

5. The theoretical number of vials required for dose preparation is the next greatest whole number of vials from the following formula:

Number of vials = Dose (mL) / 10 (mL/vial)

Example:

1. Cohort dose: 10 mg/kg
2. Subject weight: 30 kg
3. Dose for subject: 300 mg = 10 (mg/kg) × 30 (kg)
4. Dose to be added into infusion bag:

Dose (mL) = 300 mg / 50 (mg/mL) = 6.0 mL

5. The theoretical number of vials required for dose preparation:

Number of vials = 6.0 (mL) / 10.0 (mL/vial) = 1 vials

APPENDIX C**Schedule of study procedures: follow-up for subjects who have discontinued durvalumab due to toxicity in the absence of confirmed progression of disease**

Evaluation	Time Since Last Dose of durvalumab						
	Day (± 3)		Months (± 1 week)				
	30		2	3	5	7	9
Physical examination ^a	X						
Vital signs (temperature, respiratory rate, blood pressure, pulse)	X						
Weight	X						
AE/SAE assessment	X		X	X			
Concomitant medications	X		X	X			
<<World Health Organisation>> <<ECOG>> performance status ^b	X		X	X			
Subsequent anti-cancer therapy	X		X	X	X	X	X
Survival status: phone contact with subjects who refuse to return for evaluations and agree to be contacted			X	X	X	X	X
Urine hCG or serum β hCG	X						
Hematology	X		X	X			
Serum chemistry	X		X	X			
Thyroid function tests (TSH, and fT3 and fT4) ^c	X						
Tumour assessment (CT or MRI)	At the discretion of treating physician, which is not indicated until the localized bladder cancer progressed to the muscle invasive stage (T2 or above)		X				

^a Full physical exam^b PS to be collected if available at the 2 monthly calls to obtain subsequent anti-cancer therapy and survival status^c Free T3 and free T4 will only be measured if TSH is abnormal. They should also be measured if there is clinical suspicion of an adverse event related to the endocrine system.

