A population PK model was developed for durvalumab using monotherapy data from a Phase 1 study (study 1108; N=292; doses = 0.1 to 10 mg/kg Q2W or 15 mg/kg Q3W; solid tumors). Population PK analysis indicated only minor impact of body weight (WT) on PK of durvalumab (coefficient of \leq 0.5). The impact of body WT-based (10 mg/kg Q2W) and fixed dosing (750 mg Q2W) of durvalumab was evaluated by comparing predicted steady state PK

concentrations (5th, median and 95th percentiles) using the population PK model. A fixed dose of 750 mg was selected to approximate 10 mg/kg (based on median body WT of ~75 kg). A total of 1000 patients were simulated using body WT distribution of 40–120 kg. Simulation results demonstrate that body WT-based and fixed dosing regimens yield similar median steady state PK concentrations with slightly less overall between-subject variability with fixed dosing regimen.

Similar findings have been reported by others [Ng et al 2006, Wang et al. 2009, Zhang et al, 2012, Narwal et al 2013]. Wang and colleagues investigated 12 monoclonal antibodies and found that fixed and body size-based dosing perform similarly, with fixed dosing being better for 7 of 12 antibodies [3]. In addition, they investigated 18 therapeutic proteins and peptides and showed that fixed dosing performed better for 12 of 18 in terms of reducing the between-subject variability in pharmacokinetic/pharmacodynamics parameters [Zhang et al 2012].

A fixed dosing approach is preferred by the prescribing community due to ease of use and reduced dosing errors. Given expectation of similar pharmacokinetic exposure and variability, we considered it feasible to switch to fixed dosing regimens. Based on average body WT of 75 kg, a fixed dose of 750 mg Q2W durvalumab (equivalent to 10 mg/kg Q2W), 1500 mg Q4W durvalumab (equivalent to 20 mg/kg Q4W) is included in the current study. Fixed dosing of durvalumab is recommended only for subjects with > 30kg body weight due to endotoxin exposure. Patients with a body weight less than or equal to 30 kg should be dosed using a weight-based dosing schedule (Appendix B).

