5.1.3 Study drug preparation

For patients weighing ≥ 30 kg, 1500 mg Q4W durvalumab (equivalent to 20 mg/kg Q4W) (based on an average body WT of 75 kg) should be prepared. For subjects <30 kg body weight, 20 mg/kg dose should be prepared; dose is determined using body mass, calculating the stock volume of durvalumab to achieve the accurate dose according to Appendix B.

Preparation of durvalumab doses for administration with an IV bag

The dose of durvalumab for administration must be prepared by the Investigator's or site's designated IP manager using aseptic technique. Total time from needle puncture of the durvalumab vial to the start of administration should not exceed:

- 24 hours at 2°C to 8°C (36°F to 46°F)
- 4 hours at room temperature

If in-use storage time exceeds these limits, a new dose must be prepared from new vials. Infusion solutions must be allowed to equilibrate to room temperature prior to commencement of administration.

No incompatibilities between durvalumab and polyvinylchloride or polyolefin IV bags have been observed. Dose of 1500mg durvalumab for patients >30 kg will be administered using an IV bag containing 0.9% (w/v) saline with a final durvalumab concentration ranging from 1 to 20 mg/mL, and delivered through an IV administration set with a 0.2- or 0.22- μ m in-line filter.

Remove a volume of IV solution from the IV bag equal to the calculated volume of durvalumab to be added to the IV bag prior to addition of durvalumab. Next, the volume of durvalumab (ie, 15.0 mL for 750 mg or 30.0 mL for 1500 mg of durvalumab) is added to the IV bag such that final concentration is within 1 to 20 mg/mL (IV bag volumes 100 to 1000 mL). Mix the bag by gently inverting to ensure homogeneity of the dose in the bag.

Patient weight at baseline should be used for dosing calculations in patients ≤ 30 kg unless there is a $\geq 10\%$ change in weight. Dosing day weight can be used for dosing calculations instead of baseline weight per institutional standard.

For patients <30 kg, calculate the dose volume of durvalumab and number of vials needed for the subject to achieve the accurate dose according to Appendix B.

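### Appendix B states 20 mg/kg but works its only dosing example at 10 mg/kg, and sections 1.2.2, 5.1.3 and Appendix B disagree on which side of the cut-off a 30 kg subject falls

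*Combined protocol and SAP*

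**What the plan says.** **The weight-based rule.** Appendix B opens with "The durvalumab dosing should be done depending on subject weight (if subject is < 30kg) at 20 mg/kg". Section 5.1.3 agrees on the mg/kg: "For subjects <30 kg body weight, 20 mg/kg dose should be prepared". It refers to Appendix B for the volume and the number of vials.

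**The worked example.** After a general five-step formula, Appendix B gives one example. Its inputs are "Cohort dose: 10 mg/kg" and "Subject weight: 30 kg". Its results are "Dose for subject: 300 mg = 10 (mg/kg) × 30 (kg", then "Dose (mL) = 300 mg / 50 (mg/mL) = 6.0 mL", then 1 vial.

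**The cut-off.** Section 1.2.2, under Fixed Dosing, recommends fixed dosing only above 30 kg, citing endotoxin exposure, and continues: "Patients with a body weight less than or equal to 30 kg should be dosed using a weight-based dosing schedule (Appendix B". Section 5.1.3 starts with 1500 mg for patients at or above 30 kg and 20 mg/kg below 30 kg. Later in the same section, 1500 mg is for patients above 30 kg, weight-based calculations are for those at or below 30 kg, and the closing sentence returns to below 30 kg.

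**The 750 mg volume.** The bag-preparation step in section 5.1.3 gives "15.0 mL for 750 mg or 30.0 mL for 1500 mg of durvalumab". The synopsis and sections 1.4, 3.1, 5.1.2 and 6.2 give the fixed regimen as 1500 mg every 4 weeks. Section 1.2.2 has a sentence that names both 750 mg every 2 weeks and 1500 mg every 4 weeks and describes what is included in the current study.

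**The concern.** Appendix B is an operative instruction: both section 1.2.2 and section 5.1.3 send sites to it. A worked example is what a pharmacist is most likely to follow or use as a check, and this one differs by a factor of two from the rule it is meant to illustrate. Section 6.3 does not permit dose reductions, so an example at half the stated dose also sits badly with the rest of the protocol.

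The boundary matters because the dose changes sharply there, and because section 1.2.2 attaches a safety reason to it. Sections 4.1 and 4.2 set no minimum body weight, so nothing in the eligibility criteria prevents these instructions from being used. Section 10.3.5 lets the protocol itself specify what counts as an overdose, which is hard to apply where the protocol gives conflicting doses.

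**Working it through.** **Inputs.** Stated dose 20 mg/kg (Appendix B opening line; section 5.1.3). Example dose 10 mg/kg and weight 30 kg (Appendix B example). Concentration 50 mg/mL and 10 mL per vial (Appendix B formula). Fixed dose 1500 mg (section 5.1.3).

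**Formulas (Appendix B).** Dose in mg = mg/kg × kg. Volume in mL = mg ÷ 50. Vials = mL ÷ 10, rounded up.

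**Step 1: reproduce the example.** 10 × 30 = 300 mg; 300 ÷ 50 = 6.0 mL; 6.0 ÷ 10 = 0.6, rounded up to 1 vial. The printed results are correct for the 10 mg/kg input.

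**Step 2: the same subject at the stated 20 mg/kg.** 20 × 30 = 600 mg; 600 ÷ 50 = 12.0 mL; 12.0 ÷ 10 = 1.2, rounded up to 2 vials. The example is 300 ÷ 600 = one half of this. Because 10 ÷ 20 = 0.5 whatever the weight, the factor of two would apply to anyone dosed by copying the example's mg/kg.

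**Step 3: where exactly 30 kg falls.**

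| Place | Boundary as written | Group for a 30 kg subject |
|---|---|---|
| 1.2.2, Fixed Dosing | fixed > 30 kg; weight-based ≤ 30 kg | weight-based |
| 5.1.3, opening | fixed ≥ 30 kg; weight-based < 30 kg | fixed |
| 5.1.3, IV bag paragraph | fixed > 30 kg | not fixed |
| 5.1.3, weight used for calculation | weight-based ≤ 30 kg | weight-based |
| 5.1.3, closing sentence | weight-based < 30 kg | not weight-based |
| Appendix B, opening line | weight-based < 30 kg | not weight-based |
| Appendix B, example | worked for 30 kg | treated as weight-based |

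The example's subject therefore lies outside the scope in the appendix's own opening line.

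**Step 4: what the boundary is worth.** Under the opening of 5.1.3, a 30 kg subject receives 1500 mg: 1500 ÷ 50 = 30.0 mL, 3 vials, and 1500 ÷ 30 = 50 mg/kg. Under the ≤ 30 kg wording with the stated 20 mg/kg, the dose is 600 mg. The ratio is 1500 ÷ 600 = 2.5.

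**Step 5: the 750 mg volume.** 750 ÷ 50 = 15.0 mL and 1500 ÷ 50 = 30.0 mL, so both printed volumes are correct for their labels. Section 1.2.2 pairs 750 mg with 10 mg/kg every 2 weeks at 75 kg (750 ÷ 75 = 10). That is the same mg/kg as the Appendix B example, so both may be carry-over from a 2-weekly regimen. The documents do not say so.

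**The case against.** The strongest reply is that almost nobody is affected. Subjects are at least 18 years old, the fixed dose assumes an average of 75 kg, and the pharmacokinetic simulation in section 1.2.2 used weights of 40 to 120 kg. The boundary conflict touches only a subject of exactly 30 kg. The example is labelled as an example, shows its own input, and follows a generic formula, so a careful pharmacist would substitute 20 mg/kg. All of this stands, and it limits the importance of the point. It does not remove the contradiction.

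Four stronger readings are tempting but are not supported:

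- **That the example contains an arithmetic error.** It does not. The inconsistency is in its input.
- **That the protocol prescribes a five-fold range at 30 kg (300 to 1500 mg).** The ratio 1500 ÷ 300 = 5 is right, but 300 mg comes from an illustration, not a dosing rule. The intermediate 600 mg is printed nowhere: it combines the ≤ 30 kg wording with the stated 20 mg/kg. The full range also needs an adult of exactly 30 kg.
- **That the trial plainly has no 750 mg dose, or that the 15.0 mL figure endangers every subject.** The regimen statements support 1500 mg every 4 weeks only, but the sentence in section 1.2.2 on what the current study includes is ambiguous. Each volume in 5.1.3 is labelled with its dose, and nothing directs a 1500 mg subject to 15.0 mL.
- **That the 100 to 1000 mL bag range allows solutions that are too dilute.** The same sentence in 5.1.3 requires a final concentration of 1 to 20 mg/mL, which already rules out any bag volume that would breach it. For 1500 mg the whole range complies: 1500 ÷ 100 = 15 and 1500 ÷ 1000 = 1.5 mg/mL.

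**Conclusion.** The point holds as two internal inconsistencies in dose-preparation text. First, Appendix B's only worked example uses half the mg/kg that the appendix and section 5.1.3 state, for a subject outside the appendix's stated scope. Second, the 30 kg boundary changes sides between sections 1.2.2, 5.1.3 and Appendix B, and within 5.1.3. The sizes are a factor of two for anyone dosed from the example, and a factor of 2.5 between the two groups at exactly 30 kg. The second figure rests on combining the ≤ 30 kg wording with the stated 20 mg/kg.

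The practical reach is small: few if any adults in a 34-subject trial will weigh 30 kg or less. The sample size, the endpoints and the primary analysis are untouched. The text should still be corrected because sites are sent to it, one of the inconsistencies concerns a cut-off with a stated safety reason, and no entry criterion excludes low body weight. The 750 mg wording is a minor, related item. Nothing here establishes which dose or boundary is the intended one.

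**What to change.** The sponsor should decide the intended mg/kg and the intended side for exactly 30 kg, and then:

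1. Rework the Appendix B example so that it uses the same mg/kg as the stated rule, with mg, mL and vials recomputed, for a subject weight inside the appendix's scope.
2. Use one 30 kg boundary in section 1.2.2, in every sentence of section 5.1.3, and in Appendix B.
3. As a minor item, reconcile the 750 mg volume in section 5.1.3 and the sentence in section 1.2.2 that names 750 mg every 2 weeks with the 1500 mg every 4 weeks stated elsewhere.

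The cost is wording and arithmetic in three places, plus a check of any site pharmacy worksheets based on them. No change to the design, sample size or analysis is needed.

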APPENDIX D

Schedule of study procedures: follow-up for subjects who have discontinued durvalumab treatment due to confirmed progression of disease at the investigator discretion

Evaluation	Time Since Last Dose of durvalumab						
	Day (± 3)		Months (± 1 week)				
	30		2	3	5	7	9
Physical examination ^a	X						
Vital signs (temperature, respiratory rate, blood pressure, pulse)	X						
Weight	X						
AE/SAE assessment	X		X	X			
Concomitant medications	X		X	X			
<<World Health Organisation>> <<ECOG>> performance status ^b	X		X	X			
Subsequent anti-cancer therapy	X		X	X	X	X	X
Survival status: phone contact with subjects who refuse to return for evaluations and agree to be contacted			X	X	X	X	X
Urine hCG or serum β hCG	X						
Hematology	X		X	X			
Serum chemistry	X		X	X			
Thyroid function tests (TSH, and fT3 and fT4) ^c	X						
Tumour assessment (CT or MRI)	At the discretion of treating physician, which is not indicated until the localized bladder cancer progressed to the muscle invasive stage (T2 or above)		X				

^a Full physical exam

^b PS to be collected if available at the 2 monthly calls to obtain subsequent anti-cancer therapy and survival status

^c Free T3 and free T4 will only be measured if TSH is abnormal. They should also be measured if there is clinical suspicion of an adverse event related to the endocrine system.
